1.5. Rationale for Dose Selection

Sofosbuvir 400 mg, once daily, when dosed in combination with RBV with or without PEG has demonstrated broad genotypic efficacy and favorable safety profile in over 1700 HCV-infected subjects across multiple patient populations in Phase 2 and 3 trials. This dose is the approved

marketed dose of sofosbuvir for the treatment of HCV-infection and as such, has been selected for co-formulation with VEL into a fixed-dose combination tablet.

VEL 100 mg has been administered in combination with SOF 400 mg for 12 weeks to 237 HCV-infected subjects in Phase 2 studies. VEL 100 mg was selected for co-formulation with SOF and evaluation in this study based on the Phase 2 safety, PK and antiviral activity (studies GS-US-342-0102, GS-US-342-0109, and GS-US-337-0122 [Cohort 4]). The Phase 1 study GS-US-281-0102 established the anti-HCV activity of VEL and indicated that the exposures achieved following administration of doses > 25 mg provide at least 80% of maximal antiviral response in all HCV genotypes.

The favorable safety and efficacy profiles of SOF 400 mg and VEL 100 mg support further evaluation of this combination and doses in clinical development.

1.6. Overall Risk/Benefit Assessment

This study will provide information on the safety and efficacy of SOF/VEL ± RBV, a potent HCV nucleotide inhibitor and a potent HCV NS5A inhibitor, in patients with GT3 HCV infections and cirrhosis. The potential benefits of SOF/VEL ± RBV over the current standard of care for the treatment of chronic GT3 HCV in patients with cirrhosis are:

- Increasing the cure rate of GT3 HCV beyond that of currently approved therapies for patients with concomitant cirrhosis
- Providing the first PEG and RBV-free treatment option for patients with GT3 HCV and cirrhosis
- A once-daily, single tablet, single duration, pangenotypic therapy for HCV infection could simplify treatment algorithms and impact worldwide disease prevalence
- A reduction in the AEs currently associated with the use of PEG and RBV
- A short duration of therapy which should lead to better outcomes through improved adherence.

The safety profile of SOF in clinical studies includes over 1700 chronic HCV-infected subjects that have been administered ≥ 12 weeks of SOF and RBV+/-PEG-IFN. No clinical safety issues specifically related to SOF have been identified to date.

The safety profile of SOF + VEL 25mg or VEL 100mg administered for 8 or 12 weeks has been established in over 800 patients in Phase 2 studies. The safety profile of the proposed therapeutic regimen of SOF 400 mg and VEL 100 mg administered for 12 weeks has been established in 237 subjects enrolled in Phase 2 studies. No clinical safety issues specifically related to VEL or SOF + VEL have been identified to date. No clinical safety issues specifically related to the NS5A inhibitor class including daclatasvir (DCV) and LDV have been identified to date {Afdhal et al 2014b}, {Afdhal et al 2014a}, {Kowdley et al 2014}.

The safety profile of SOF/VEL has been studied in 4 Phase 3 trials (ASTRAL 1-4) in 1302 patients. Twelve weeks of SOF/VEL was generally well tolerated, and led to a similar incidence of AEs and SAEs compared to placebo in patients with GT 1, 2, 4, 5, or 6 HCV. When 12 weeks of SOF/VEL was compared to SOF + RBV for 12 or 24 weeks in patients with GT2 or 3 HCV, therapy with SOF/VEL was again well tolerated with few differences in AEs or SAEs, minus the avoidance of RBV associated toxicities. Patients who received SOF/VEL for either 12 or 24 weeks with decompensated cirrhosis experienced AEs and SAEs typical for patients with decompensated cirrhosis in no pattern that could be attributed to study drug. Patients with decompensated cirrhosis who received SOF/VEL + RBV for 12 weeks also experienced AEs and SAEs consistent with underlying liver disease as well as toxicities expected with RBV treatment.

In summary, SOF/VEL ± RBV has the potential to increase SVR12 rates of GT3 HCV infections among patients with cirrhosis. If high rates of SVR can be obtained with a short, PEG-free ± RBV regimen, the anticipated improvements in safety and tolerability would offer a favourable risk-benefit determination for patients with chronic GT3 HCV infection and cirrhosis.

1.7. Compliance

This study will be conducted in compliance with this protocol, Good Clinical Practice (GCP), and all applicable regulatory requirements.

2. OBJECTIVES

The primary objectives of this study are:

- To evaluate the efficacy of study treatment with Sofosbuvir/Velpatasvir (SOF/VEL) FDC and SOF/VEL FDC and Ribavirin (RBV) for 12 weeks as measured by the proportion of subjects with sustained virologic response 12 weeks after cessation of treatment regimen (SVR12)
- To evaluate the safety and tolerability of each treatment regimen

The secondary objectives of this study are:

- To determine the proportion of subjects who attain SVR at 4 weeks after cessation of each treatment regimen (SVR4)
- To evaluate the kinetics of circulating HCV RNA during treatment and after cessation of each treatment regimen
- To evaluate the emergence of viral resistance to SOF and VEL during treatment and after cessation of study treatment regimen

The exploratory objective of this study is:

- PPD

3. STUDY DESIGN

3.1. Treatment Plan and Regimen

This is a multicenter, randomized, open-label study that will evaluate the safety, tolerability and antiviral efficacy of SOF/VEL FDC with and without RBV for 12 weeks in subjects with chronic genotype 3 HCV infection and compensated cirrhosis with or without HIV co-infection.

Approximately 200 subjects with chronic genotype 3 HCV infection and compensated cirrhosis will be randomized (1:1) to either:

- Group 1 (n = 100): SOF/VEL once daily for 12 weeks

OR

- Group 2 (n = 100): SOF/VEL + RBV for 12 weeks

Randomization will be stratified by prior treatment experience (treatment naïve/treatment-experienced).

3.2. Visit Schedule

All subjects will complete screening, on-treatment, and post-treatment assessments.

Screening assessments will be completed within 28 days of the Day 1 visit. The screening window can be extended to 42 days for subjects requiring liver biopsy, additional HCV genotyping or for extenuating circumstances.

All subjects will complete the following study visits: Screening, Baseline/Day 1, on-treatment visits at the end of Weeks 2, 4, 8 and 12. All subjects will complete the post-treatment Week 4 visit. Subjects with HCV RNA < LLOQ at the post-treatment Week 4 visit will complete the post-treatment Week 12 visit. Subjects with HCV RNA \geq LLOQ at post-treatment Week 12 visit will be asked to return for a confirmatory visit.

The assessments performed at each visit are described in Section 6 and shown in [Appendix 2](#).

3.3. Virologic Response

3.3.1. HCV Virologic Response-Based Treatment Stopping Criteria

The following on-treatment HCV virologic response-based treatment stopping criteria will be utilized:

- Confirmed HCV RNA \geq LLOQ after 2 consecutive HCV RNA < LLOQ
- Confirmed > 1 log₁₀ increase from nadir
- HCV RNA \geq LLOQ through 12 weeks of treatment

Confirmation should be performed as soon as possible and must occur no later than 2 weeks after an initial observation indicating virologic failure.

If HCV viral relapse is detected at post-treatment Week 4 or 12 visits, subjects will be asked to return for a confirmatory visit.

3.3.2. HIV Virologic Rebound Criteria

[figure not shown]
Subjects who have at least two consecutive post-baseline visit plasma HIV-1 RNA levels ≥ 400 copies/mL (at least two weeks apart) will be considered to have HIV virologic rebound.

Following an initial HIV-1 RNA result of ≥ 400 copies/mL, subjects will continue to take their current ARV regimen and be asked to return to the clinic after 2 weeks for a scheduled or unscheduled blood draw for confirmation of HIV virologic rebound. If HIV virologic rebound is confirmed at the scheduled or unscheduled visit, the blood samples from this visit will be used for HIV-1 genotype/phenotype testing. If no resistance to the subject's current ARV regimen is detected, the subject may continue on current ARV regimen. If resistance to the subject's current ARV regimen is detected, then it is strongly recommended that whenever possible, the subject be switched to an alternative approved regimen, as outlined in Section 4.2 of this protocol.

HCV study drug should be continued unless safety events warrant the discontinuation of the study drug, as outlined in Section 3.5 of the protocol, or if a subject must be switched to an unapproved HIV regimen based upon acquired resistance.

Please refer to [Figure 3-1](#) for the management of subjects who meet the criteria for HIV virologic rebound.

Figure 3-1. HIV Virologic Rebound Schema

- a HCV study drug should be continued unless safety events warrant the discontinuation of these study drugs, as outlined in Section 3.5 of the protocol
- b If virologic rebound is not confirmed, the subject should remain on their current ARV regimen.
- c If virologic rebound is confirmed, the HIV-1 genotype and phenotype (reverse transcriptase and protease) will be analyzed.
- d Based on the results of the genotype and phenotype assays, the subject may remain on their ARV regimen at the discretion of the Investigator (e.g. virologic rebound due to non-adherence). If the genotype and/or phenotype assay fails to provide results, a new ARV regimen may be configured at the discretion of the Investigator in consultation with the Medical Monitor.
- e A new ARV regimen should be configured or the ARV regimen held for the duration of SOF/VEL dosing at the Investigator's discretion in consultation with the Medical Monitor. If a new ARV regimen is required, it is strongly recommended to use an alternative regimen that is approved in this protocol. If an unapproved ARV regimen is prescribed, then SOF/VEL ± RBV must be discontinued after consultation with the medical monitor.

3.4. Stopping Rules for Individual Subjects

Subjects who meet any of the following criteria should be discontinued from the study and complete an Early Termination Visit and return for Posttreatment Follow-up visits:

- Elevation of ALT and/or AST that is greater than the ULN and $> 5x$ baseline or nadir confirmed by immediate repeat testing unless laboratory results are assessed by both the investigator and Gilead Medical Monitor as having an explanation other than drug induced liver injury and it is deemed in the best interest of the subject to continue HCV treatment
- Confirmed elevation of ALT $>15 x$ ULN (unrelated to any interventional procedures)
- Confirmed total bilirubin $>10 x$ ULN (unrelated to any interventional procedures)
- Confirmed total bilirubin $>3x$ baseline or $3x$ nadir (unrelated to any interventional procedures)
- Any Grade 3 or greater rash associated with constitutional symptoms
- Any non-laboratory Grade 4 events assessed as related to administration of SOF/VEL
- Worsening of disease state as evidenced by progressing hepatic decompensation and/or progression of Child-Pugh Score (CPT) to ≥ 10

The Gilead Medical Monitor should be consulted prior to discontinuation of SOF/VEL and /or RBV unless the investigator believes that immediate action is warranted to ensure the continued safety of the subject.

Any questions regarding toxicity management should be directed to Gilead Medical Monitor.

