4.3. Exclusion Criteria

Subjects who meet *any* of the following exclusion criteria are not to be enrolled in this study.

1. Current or prior history of any of the following:
 - a. Clinically-significant illness (other than HCV or HIV) or any other major medical disorder that may interfere with subject treatment, assessment or compliance with the protocol; subjects currently under evaluation for a potentially clinically-significant illness (other than HCV/HIV) are also excluded.
 - b. Gastrointestinal disorder or postoperative condition that could interfere with the absorption of the study drug.
 - c. Difficulty with blood collection and/or poor venous access for the purposes of phlebotomy.
 - d. Solid organ or bone marrow transplantation.
 - e. Significant pulmonary disease, significant cardiac disease, or porphyria.
 - f. Clinically significant hemoglobinopathy (e.g., sickle cell disease, thalassemia).
 - g. Psychiatric hospitalization, suicide attempt, and/or a period of disability as a result of their psychiatric illness within the last 5 years. Subjects with psychiatric illness (without the prior mentioned conditions) that is well-controlled on a stable treatment regimen for at least 12 months prior to enrollment or has not required medication in the last 12 months may be included.
 - h. Malignancy within the 5 years prior to screening, with the exception of specific cancers that have been cured by surgical resection (basal cell skin cancer, etc). Subjects under evaluation for possible malignancy are not eligible.

- i. Active, serious infection (other than HIV or HCV) requiring parental antibiotics, antivirals or antifungals within 30 days prior to baseline.
2. Child-Pugh-Turcotte (CPT) Score >7 at Screening
3. Current, uncontrolled ascites, variceal hemorrhage, hepatic encephalopathy, hepatorenal syndrome, hepatopulmonary syndrome, or other signs of decompensated cirrhosis
4. Screening ECG with clinically significant abnormalities
5. Subjects with the following laboratory parameters at screening:
 - HIV-1 RNA >50 copies/mL
 - CD4 T-cell count <100 cells/mm³
 - ALT > 10 × the upper limit of normal (ULN)
 - AST > 10 × ULN
 - Direct bilirubin > 1.5 × ULN
 - For subjects receiving ritonavir boosted atazanavir regimen, a direct bilirubin > 1.5 x ULN will be allowed if < 25% of the total bilirubin
 - Platelets < 50,000/μL
 - HbA1c > 8.5%
 - Creatinine clearance (CLcr) < 60 mL /min as calculated by the Cockcroft-Gault equation {Cockcroft et al 1976}

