6.3.3. Weeks 4 and 8 (\pm 3 days)

The following procedures/assessments are to be completed at the end of Weeks 4 and 8:

- Obtain vital signs (resting blood pressure, pulse, respiratory rate and temperature)
- Assessment of AEs and concomitant medications
- Conduct pregnancy prevention counseling
- Obtain blood samples for:
 - Hematology
 - Chemistry
 - HCV RNA
 - Viral sequencing
 - PK sample
 - HIV-1 RNA will only be collected and analyzed for co-infected subjects
- Obtain urine sample for pregnancy test (for females of child bearing potential only)
- Assess adherence with study drug dosing regimen including pill count
- Dispense study drugs as directed by the IWRS

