8.2.2. Assessment of Severity

The severity grading of AEs will be assessed as Grade 1, 2, 3, or 4 using the GSI Grading Scale for Severity of Adverse Events and Laboratory Abnormalities ([Appendix 3](#)). For AEs associated with laboratory abnormalities, the event should be graded on the basis of the clinical severity in the context of the underlying conditions; this may or may not be in agreement with the grading of the laboratory abnormality.

8.3. Investigator Requirements and Instructions for Reporting Adverse Events and Serious Adverse Events to Gilead

Requirements for collection prior to study drug initiation:

- After informed consent, but prior to initiation of study medication, the following types of events should be reported on the case report form (eCRF): all SAEs and adverse events related to protocol-mandated procedures.

Adverse Events

- Following initiation of study medication, all AEs, regardless of cause or relationship, pregnancy and other special situation reports, until 30 days after last administration of study drug must be collected/ reported to the eCRF database as instructed.
- All AEs should be followed up until resolution or until the adverse event is stable, if possible. Gilead Sciences may request that certain AEs be followed beyond the protocol defined follow up period.

Serious Adverse Events

- All SAEs, regardless of cause or relationship, that occurs after the subject first consents to participate in the study (ie, signing the informed consent) and throughout the duration of the study, including the protocol-required post-treatment follow-up period, must be reported to the eCRF database and Gilead Drug Safety and Public Health (DSPH) as instructed. This also includes any SAEs resulting from protocol-associated procedures performed after informed consent is signed.

- Any SAEs and deaths that occur after the post-treatment follow-up visit but within 30 days of the last dose of study drug, regardless of causality, should also be reported.
- Investigators are not obligated to actively seek SAEs after the protocol defined follow up period, however, if the investigator learns of any SAEs that occur after study participation has concluded and the event is deemed relevant to the use of IMP, he/she should promptly document and report the event to Gilead DSPH.
- All AEs and SAEs will be recorded in the eCRF database within the timelines outlined in the eCRF completion guideline.

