Hypocalcemia (corrected for albumin if appropriate*) Adult and Pediatric ≥2 Years	7.8 <LLN mg/dL 1.94 to <LLN mmol/L	7.0 to <7.8 mg/dL 1.74 to <1.94 mmol/L	6.1 to <7.0 mg/dL 1.51 to <1.74 mmol/L	<6.1 mg/dL <1.51 mmol/L
Pediatric ≥7 days -2 Years	7.8 to 8.4 mg/dL 1.94 to 2.10 mmol/L	7.0 to <7.8 mg/dL 1.74 to <1.94 mmol/L	6.1 to <7.0 mg/dL 1.51 to <1.74 mmol/L	<6.1 mg/dL <1.51 mmol/L
Infant, <7 Days	6.5 to 7.5 mg/dL 1.61 to 1.88 mmol/L	6.0 to <6.5 mg/dL 1.49 to <1.61 mmol/L	5.5 to <6.0 mg/dL 1.36 to <1.49 mmol/L	<5.5 mg/dL <1.36 mmol/L
Hypercalcemia (corrected for albumin if appropriate*) Adult and Pediatric ≥7 Days	>ULN to 11.5 mg/dL >ULN to 2.88 mmol/L	>11.5 to 12.5 mg/dL >2.88 to 3.13 mmol/L	>12.5 to 13.5 mg/dL >3.13 to 3.38 mmol/L	>13.5 mg/dL >3.38 mmol/L
Infant, <7 Days	11.5 to 12.4 mg/dL 2.86 to 3.10 mmol/L	>12.4 to 12.9 mg/dL >3.10 to 3.23 mmol/L	>12.9 to 13.5 mg/dL >3.23 to 3.38 mmol/L	>13.5 mg/dL >3.38 mmol/L
Hypocalcemia (ionized)	3.0 mg/dL to <LLN 0.74 mmol/L to <LLN	2.5 to <3.0 mg/dL 0.62 to <0.74 mmol/L	2.0 to <2.5 mg/dL 0.49 to <0.62 mmol/L	<2.0 mg/dL <0.49 mmol/L
Hypercalcemia (ionized)	>ULN to 6.0 mg/dL	>6.0 to 6.5 mg/dL	>6.5 to 7.0 mg/dL	>7.0 mg/dL
	>ULN to 1.50 mmol/L	>1.50 to 1.63 mmol/L	>1.63 to 1.75 mmol/L	>1.75 mmol/L
Hypomagnesemia	1.40 to <LLN mg/dL 1.2 to <LLN mEq/L	1.04 to <1.40 mg/dL 0.9 to <1.2 mEq/L	0.67 to <1.04 mg/dL 0.6 to <0.9 mEq/L	<0.67 mg/dL <0.6 mEq/L
	0.58 to <LLN mmol/L	0.43 to <0.58 mmol/L	0.28 to <0.43 mmol/L	<0.28 mmol/L

CHEMISTRY				
	Grade 1	Grade 2	Grade 3	Grade 4
Hypophosphatemia Adult and Pediatric > 14 Years	2.0 to < LLN mg/dL 0.63 to < LLN mmol/L	1.5 to < 2.0 mg/dL 0.47 to < 0.63 mmol/L	1.0 to < 1.5 mg/dL 0.31 to < 0.47 mmol/L	< 1.0 mg/dL < 0.31 mmol/L
Pediatric 1 Year–14 Years	3.0 to < LLN mg/dL 0.96 to < LLN mmol/L	2.5 to < 3.0 mg/dL 0.80 to < 0.96 mmol/L	1.5 to < 2.5 mg/dL 0.47 to < 0.80 mmol/L	< 1.5 mg/dL < 0.47 mmol/L
Pediatric < 1 Year	3.5 to < LLN mg/dL 1.12 to < LLN mmol/L	2.5 to < 3.5 mg/dL 0.80 to < 1.12 mmol/L	1.5 to < 2.5 mg/dL 0.47 to < 0.80 mmol/L	< 1.5 mg/dL < 0.47 mmol/L
Hyperbilirubinemia Adult and Pediatric > 14 Days	> 1.0 to 1.5 × ULN	> 1.5 to 2.5 × ULN	> 2.5 to 5.0 × ULN	> 5.0 × ULN
Infant, ≤ 14 Days (non-hemolytic)	NA	20.0 to 25.0 mg/dL 342 to 428 μmol/L	> 25.0 to 30.0 mg/dL > 428 to 513 μmol/L	> 30.0 mg/dL > 513 μmol/L
Infant, ≤ 14 Days (hemolytic)	NA	NA	20.0 to 25.0 mg/dL 342 to 428 μmol/L	> 25.0 mg/dL > 428 μmol/L

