Alkaline Phosphatase	1.25 to 2.50 × ULN	> 2.50 to 5.00 × ULN	> 5.00 to 10.00 × ULN	> 10.00 × ULN
Total Amylase	> 1.0 to 1.5 × ULN	> 1.5 to 2.0 × ULN	> 2.0 to 5.0 × ULN	> 5.0 × ULN
Pancreatic Amylase	> 1.0 to 1.5 × ULN	> 1.5 to 2.0 × ULN	> 2.0 to 5.0 × ULN	> 5.0 × ULN
Lipase	> 1.0 to 1.5 × ULN	> 1.5 to 3.0 × ULN	> 3.0 to 5.0 × ULN	> 5.0 × ULN
Albumin Pediatrics <16 years	-	2.0 to < LLN g/dL 20 to < LLN g/L	< 2.0 g/dL < 20 g/L	NA
≥ 16 years	3.0 g/dL to < LLN 30 g/L to < LLN	2.0 to < 3.0 g/dL 20 to < 30 g/L	< 2.0 g/dL < 20 g/L	NA

URINALYSIS				
	Grade 1	Grade 2	Grade 3	Grade 4
Hematuria (Dipstick)	1+	2+	3-4+	NA
Hematuria (Quantitative) See Note below				
Females	>ULN - 10 RBC/HPF	> 10-75 RBC/HPF	> 75 RBC/HPF	NA
Males	6-10 RBC/HPF	> 10-75 RBC/HPF	> 75 RBC/HPF	NA
Proteinuria (Dipstick)	1+	2-3+	4+	NA
Proteinuria, 24 Hour Collection				
Adult and Pediatric ≥ 10 Years	200 to 999 mg/24 h	>999 to 1999 mg/24 h	>1999 to 3500 mg/24 h	> 3500 mg/24 h
Pediatric > 3 Mo to < 10 Years	201 to 499 mg/m ² /24 h	>499 to 799 mg/m ² /24 h	>799 to 1000 mg/m ² /24 h	> 1000 mg/ m ² /24 h
Glycosuria (Dipstick)	1+	2-3+	4+	NA

Notes:

- Toxicity grades for Quantitative and Dipstick Hematuria will be assigned by Covance Laboratory, however for other laboratories, toxicity grades will only be assigned to Dipstick Hematuria.
- With the exception of lipid tests, any graded laboratory test with a result that is between the LLN and ULN should be assigned Grade 0.
- If the severity of a clinical AE could fall under either one of two grades (e.g., the severity of an AE could be either Grade 2 or Grade 3), select the higher of the two grades for the AE.

CARDIOVASCULAR				
	Grade 1	Grade 2	Grade 3	Grade 4
Cardiac Arrhythmia (general) (By ECG or physical exam)	Asymptomatic AND No intervention indicated	Asymptomatic AND Non-urgent medical intervention indicated	Symptomatic, non-life-threatening AND Non-urgent medical intervention indicated	Life-threatening arrhythmia OR Urgent intervention indicated
Cardiac-ischemia/Infarction	NA	NA	Symptomatic ischemia (stable angina) OR Testing consistent with ischemia	Unstable angina OR Acute myocardial infarction
Hemorrhage (significant acute blood loss)	NA	Symptomatic AND No transfusion indicated	Symptomatic AND Transfusion of ≤ 2 units packed RBCs (for children ≤ 10 cc/kg) indicated	Life-threatening hypotension OR Transfusion of > 2 units packed RBCs indicated (for children ≤ 10 cc/kg) indicated

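### The relative total bilirubin stopping rule has no above-ULN condition, so a confirmed normal value can meet it when baseline or nadir is below one third of the ULN

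*Protocol*

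**What the plan says.** Protocol Section 3.4 states that a subject who meets any one of its criteria should be discontinued, complete an Early Termination visit and return for post-treatment follow-up. Two of its bullets use change relative to the subject's own values:

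- **ALT/AST.** The bullet opens "Elevation of ALT and/or AST that is greater than the ULN" and also requires more than 5x baseline or nadir on immediate repeat testing. It can be waived if the investigator and the Medical Monitor both find an explanation other than drug-induced liver injury and judge that continuing is best for the subject.
- **Total bilirubin.** "Confirmed total bilirubin $>3x$ baseline or $3x$ nadir (unrelated to any interventional procedures"). Its only exception is for interventional procedures.

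A separate bullet sets an absolute limit of 10x ULN for total bilirubin. It does not restrict the relative one.

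On consultation, Section 3.4 says "The Gilead Medical Monitor should be consulted prior to discontinuation of SOF/VEL and /or RBV", unless the investigator believes immediate action is needed for safety. Section 3.7 is firmer: the Medical Monitor must be consulted before a subject is discontinued, when that is medically feasible. Sections 7.3.1 and 7.4 only refer back to Section 3.4. Sections 3.5 and 3.7 add no ULN condition.

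In Appendix 3 the row "Hyperbilirubinemia Adult and Pediatric > 14 Days" starts Grade 1 above 1.0 x ULN. The notes add that, lipid tests aside, "any graded laboratory test with a result that is between the LLN and ULN should be assigned Grade 0". The bilirubin exclusion at screening (Section 4.3) is "Direct bilirubin > 1.5 × ULN"; there is no lower limit on total bilirubin.

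**The concern.** A rule based only on a multiple of a low starting value can fire while the result is still normal. The ALT/AST bullet guards against this by requiring the value to exceed the ULN. The bilirubin bullet has no such guard, and no other section supplies one. Read literally, it tells the investigator to discontinue a subject on a confirmed value that the protocol's own scale grades 0.

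What is at stake is an individual subject's 12-week antiviral course. Chemistry is drawn at Week 2 and again at the visit for which "The following procedures/assessments are to be completed at the end of Weeks 4 and 8", so a trigger at a scheduled visit can fall well before the planned end of treatment.

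**Working it through.** The plan gives no figure on this point to reproduce. The check is an inequality on the written rule.

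**Inputs**

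- Trigger: confirmed total bilirubin T > 3 x baseline or 3 x nadir (Section 3.4). Either reference suffices, so let r be the lower of the two.
- Grade 0: T between LLN and ULN; Grade 1 begins above 1.0 x ULN (Appendix 3).
- Treatment length: 12 weeks = 84 days; on-treatment chemistry at Weeks 2, 4, 8 and 12 (Sections 6.3.2 to 6.3.4, Appendix 2).
- ULN for total bilirubin in mg/dL: not given. Assumed range 1.0 to 1.3 mg/dL.

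**Step 1: when an in-range trigger exists.** A value with T > 3r and T ≤ ULN exists if and only if 3r < ULN, that is r < ULN/3 = 0.333 x ULN.

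**Step 2: where the rule fires, in ULN units.**

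| Baseline or nadir | Trigger today | Trigger with an above-ULN clause | Shift |
|---|---|---|---|
| 0.30 | > 3 x 0.30 = 0.90 | > 1.00 | 0.10 |
| 0.25 | > 3 x 0.25 = 0.75 | > 1.00 | 0.25 |
| 0.20 | > 3 x 0.20 = 0.60 | > 1.00 | 0.40 |

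**Step 3: the same in mg/dL under the assumed ULN.** ULN/3 is 0.33, 0.37, 0.40 and 0.43 mg/dL for a ULN of 1.0, 1.1, 1.2 and 1.3.

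- r = 0.2 fires above 0.6 mg/dL (0.46 to 0.60 x ULN), in range throughout.
- r = 0.3 fires above 0.9 mg/dL (0.69 to 0.90 x ULN), in range throughout.
- r = 0.4 fires above 1.2 mg/dL, in range only if the ULN is 1.3.
- r = 0.5 fires above 1.5 mg/dL, out of range throughout.

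**Step 4: what the clause changes.** The trigger becomes T > max(ULN, 3r). For r ≥ ULN/3 the maximum is 3r and nothing changes. For r < ULN/3, only values in (3r, ULN] stop triggering. Every above-ULN value that triggers today still triggers.

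**Step 5: treatment remaining at a scheduled trigger.** Week 2: 84 − 14 = 70 days. Week 4: 84 − 28 = 56. Week 8: 84 − 56 = 28. Week 12: 0. These are calendar figures before any delay for confirmation or consultation, not estimates of treatment lost. On scheduled visits alone, the Week 2 reference is the baseline, and an earlier on-treatment nadir can serve from Week 4. An unscheduled visit (Section 6.3.5) could supply a nadir sooner.

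**The case against.** The strongest reply is that nobody would stop treatment this way. The result has to be confirmed, and the Medical Monitor should be consulted (Section 3.4) or must be when medically feasible (Section 3.7). The bypass for immediate safety action is hard to invoke for a normal bilirubin. Two clinicians would therefore normally see an in-range value before treatment stopped. This stands as substantial mitigation. It does not cure the wording: confirmation shows the value is real, not that it is abnormal, and consultation comes with no threshold. The ALT/AST bullet has an explicit waiver; this one does not.

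A second reply is that the documents give neither a bilirubin ULN nor a baseline distribution for this compensated-cirrhosis population. Nothing shows that even one of about 200 subjects would be affected. That is correct, and no frequency is asserted.

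A third is that a sponsor may want a more sensitive bilirubin trigger in cirrhosis, so the asymmetry need not be an oversight. Intent cannot be established either way. But sensitivity is a weak reason to stop curative treatment on a normal value, and the clause gives up no above-ULN signal.

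A reader might also infer that the gap matters more here than it would for ALT/AST, because a 3x multiplier leaves in-range triggers below 0.333 x ULN and a 5x multiplier only below 0.200 x ULN. Those figures compare multipliers, not risks. Risk depends on where each analyte lies and how it moves on treatment, which the documents do not report.

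**Conclusion.** The point holds and is minor. As written, a confirmed Grade 0 total bilirubin meets a discontinuation criterion whenever baseline or nadir is below ULN/3, and eligibility does not exclude such subjects. The threshold is exact in ULN units; the mg/dL equivalent of 0.33 to 0.43 rests on the assumed ULN of 1.0 to 1.3. Confidence is high about the wording and the arithmetic. Practical importance is probably small, and its frequency is not derivable.

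Three stronger conclusions might be inferred, and the documents do not support them:

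- **An effect on SVR12.** Nothing indicates how many subjects would stop early for this reason, and Sections 3.4 and 3.5 keep those who stop in post-treatment follow-up.
- **A distorted primary safety endpoint.** Section 8.1.3 requires laboratory abnormalities that lead to discontinuation to be recorded as AEs, but whether a normal value counts as one is not settled. A mismatch between AE grade and laboratory grade is already accepted in Section 8.2.2: "this may or may not be in agreement with the grading of the laboratory abnormality".
- **More such stops in Group 2.** The protocol attributes bilirubin rises in earlier ribavirin arms to hemolysis, but those reports concern Grade 3 or 4 elevations and say nothing about in-range changes.

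**What to change.** Replace the fourth bullet of Protocol Section 3.4 with: *Confirmed total bilirubin greater than the ULN and >3x baseline or nadir (unrelated to any interventional procedures)*. Placing the ULN condition before a single multiple that covers both references makes it apply to baseline and nadir alike. Leave the other bullets, including the 10x ULN limit and the decompensation rule, as they are.

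The cost is one clause. It needs no new test, visit or table and no SAP change, and it loses no above-ULN signal.
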